8.3. Subject Disposition

Subject disposition for randomized Subjects will be presented by:

- Summary of Subjects per visit
- Summary of early withdrawal and reason for early withdrawal.

In addition, Subjects enrolled and not implanted, or withdrawing prior to randomization, will be summarized.

8.4. Demographics and Baseline Characteristics

Demographics and baseline characteristics of the data set will be summarized by randomization group. These parameters will include (but not be limited to):

- Age
- Gender
- Ethnicity
- BMI
- Medical history
- Low Back pain descriptive characteristics
- Duration of back pain
- Work status (including duration of “off work” and “part time” status for those Subjects adversely affected by back pain)
- Low Back pain medications and concomitant medications

8.5. Primary Efficacy Endpoint

8.5.1. Primary Analysis

The Primary Efficacy Endpoint is a comparison of responder rates between Treatment and Control groups, where a “responder” is a Subject with $\geq 30\%$ reduction from baseline in average low back pain VAS, without any increase from baseline in pain medication and/or muscle relaxants prescribed and taken in the two weeks prior to the Primary Endpoint Assessment Visit.

Note: The primary outcome measure is intended to assess the efficacy of 120 days of stimulation. Thus the visit for assessment of the primary outcome must occur no sooner than 120 days post randomization.

The primary efficacy endpoint will be assessed by the following hypotheses:

$H_0: \pi_{VAS_T} = \pi_{VAS_C}$

$H_A: \pi_{VAS_T} \neq \pi_{VAS_C}$,

where π_{VAS_T} is the proportion of Subjects meeting primary success criteria in the Treatment group and π_{VAS_C} is the proportion of Subjects meeting success criteria in the Control group. The hypotheses will be tested using a two-sided binomial test for a difference in proportions. The objective will be met if a statistically significant difference favoring the Treatment group is found.

The study will be considered a success if the primary efficacy endpoint is met.

For the primary analysis in the ITT population, the impact of Subjects with missing endpoint assessment will be examined in sensitivity analyses.

Records of pain medications will be collected along with all other medications used for treatment of low back pain, which are also being collected for analysis of secondary and cost-effectiveness endpoints. The Subject will report medications taken at each scheduled follow-up visit. Rescue medications taken on an exceptional basis for acute pain conditions other than back pain will also be documented and their possible effect examined as part of sensitivity analyses.

The number and percent of randomized Subjects meeting the responder criteria will be presented by randomization group with associated 95% asymptotic confidence limits. The difference in proportions and associated 95% confidence limits will be presented along with the p-value from a binomial test for the test of the hypothesis associated with the primary objective.

The individual components of the primary efficacy endpoint (VAS and medications) will be analyzed and presented separately. Cumulative proportion of responder analysis will also be used as a way of presenting this data.

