5.1. Randomization

Subjects will be randomized at the Randomization Visit 14 ± 3 days post implant. Subsequent visits are scheduled relative to the date of randomization with the primary efficacy endpoint assessed at the Primary Endpoint Assessment Visit. Randomization will be performed according to a random permuted block design stratified by clinical site with a 1:1 allocation ratio for Treatment vs. Control.

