6.1. Sample Size Estimate

The sample size for the study is determined under the following assumptions for the primary efficacy endpoint:

- Minimum power of 80%
- Type I error of 5%
- Assumed primary efficacy success in Treatment group: 50%
- Assumed primary efficacy success in Control group: 25%

Under the above assumptions, a minimum of 116 evaluable Subjects is required in order to demonstrate superiority of the ReActiv8 treatment. The total sample size is increased by 10% to 128 to allow for attrition. The total sample size may be increased, but not decreased, at the time of the planned interim analysis to adjust for updates to the planning assumptions.

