6.2. Level of Power and Significance

All tests of significance will be performed at the two-sided 0.05 significance level. The hypotheses associated with the first five secondary efficacy objectives will be tested using the Hochberg multiple comparison adjustment in the event the primary efficacy objective is met.

7. Data Structure and Handling

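### Randomisation is stratified by site but the primary test and its limits ignore site: valid, but conservative and less efficient if sites differ substantially

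*SAP*

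**What the plan says.** SAP 5.1 states: "Randomization will be performed according to a random permuted block design stratified by clinical site with a 1:1 allocation ratio for Treatment vs. Control". SAP 5 and the protocol synopsis (Table 1) say the same. The block size is not given. Up to 40 sites are planned.

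The primary analysis in SAP 8.5.1 is a comparison of two proportions: "The hypotheses will be tested using a two-sided binomial test for a difference in proportions". For estimation, "The difference in proportions and associated 95% confidence limits will be presented along with the p-value from a binomial test". Protocol 4.7.1.1 specifies the same test. Under SAP 6.2, "All tests of significance will be performed at the two-sided 0.05 significance level".

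Site enters the analysis elsewhere:

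- SAP 7.4 tests for a common odds ratio across sites. If p is below 0.15, it allows exploratory covariate modelling, possibly with site as a random effect. If poolability is not shown, primary results may be presented by groups of sites.
- Protocol 2.4 mentions an analysis by site.

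Neither replaces or adjusts the primary test.

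**The concern.** Blocking within site balances the arms on whatever makes one site's response rate differ from another's. The true sampling variance of the difference between arms then largely excludes the between-site component. The pooled binomial variance still includes it. When sites differ, the calculated standard error is therefore too large, the test runs below its nominal 5%, and the limits are wider than they need be.

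Substantial site differences are plausible. The trial is international, investigators come from several specialties (Protocol 4.4.1), the outcome is subjective, and response may depend on implantation and programming. The single primary test decides whether the study succeeds, and it gates the five secondary hypotheses (SAP 8.6), so avoidable imprecision in it is worth removing.

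**Working it through.** **Inputs from the documents.** Responder rates 50% and 25%, two-sided 5%, 80% power, 116 evaluable Subjects (SAP 6.1 and 6.2); up to 40 sites (SAP 5); maximum size 2 × 116 = 232 (SAP 8.7).

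**Assumptions not in the documents.** Between-site standard deviation (SD) on the logit scale, varied from 0 to 1.5; block size 4; unequal site sizes. For scale, with a 25% control rate overall, SD 0.5 puts the 10th and 90th percentile sites at about 14% and 37%. SD 1.0 puts them at about 7% and 49%.

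**1. The plan's own figure.** Using the unstratified test with pooled variance and no continuity correction:

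n per arm = [1.960 √(2 × 0.375 × 0.625) + 0.842 √(0.50 × 0.50 + 0.25 × 0.75)]² / 0.25² = (1.342 + 0.557)² / 0.0625 ≈ 57.7, so 58 per arm and 116 in all.

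This matches SAP 6.1. Power at 58 per arm is 80.2%.

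**2. Why the planned test is conservative.** Let p_s be the response rate at site s and p the overall rate. Then p(1 − p) = mean of p_s(1 − p_s) + variance of p_s. The binomial test uses the left side; stratified blocks remove most of the last term from the real variance. If R is the ratio of calculated to true standard error, the two-sided error is about 2[1 − Φ(1.96 R)].

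In simulation under a 25%/25% null (8,000 runs per scenario; 10, 20 and 40 sites), R was:

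- 0.99 to 1.01 at SD 0.5 or less: no visible effect.
- 1.04 to 1.05 at SD 1.0: the formula gives 4.2% to 4.0%; simulated 3.8 to 4.3%.
- 1.11 to 1.12 at SD 1.5: the formula gives 3.0% to 2.8%; simulated 2.9 to 3.0%.

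Under a 35%/35% null (3,000 runs) the planned test's error was 2.9 to 3.8% at SD 1.0 to 1.2. A Cochran-Mantel-Haenszel (CMH) test with sites under 6 Subjects merged gave 3.9 to 5.1%.

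**3. Every site as its own stratum.** Power at 50% v 25%, planned test v CMH, 40 sites: SD 0, 80.8 v 75.2; SD 0.5, 81.8 v 77.4; SD 1.0, 81.6 v 81.0; SD 1.5, 83.0 v 85.9. With 116 / 40 = 2.9 Subjects per site, sites with a single Subject or a single arm contribute nothing. About 88% of the information remains. This version is worse than the plan unless sites differ very strongly.

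**4. Small sites merged.** Sites under 6 Subjects form one stratum. Power at 50% v 25%, planned test v merged CMH, 3,000 runs, Monte Carlo standard error about 0.7 points:

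| Site SD (logit) | 40 sites | 25 sites | 15 sites |
|---|---|---|---|
| 0 | 80.5 v 80.0 | 80.9 v 80.6 | 79.9 v 79.7 |
| 0.5 | 81.9 v 81.9 | 82.5 v 82.6 | 80.4 v 81.3 |
| 0.7 | 81.0 v 81.7 | 81.3 v 82.7 | 82.5 v 83.6 |
| 1.0 | 82.8 v 83.9 | 82.6 v 85.0 | 82.0 v 85.0 |
| 1.2 | 80.9 v 83.1 | 82.2 v 85.4 | 82.7 v 86.7 |

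The gain at SD 1.0 to 1.2 is 1.1 to 2.2 points with 40 sites, 2.4 to 3.2 with 25, and 3.0 to 4.0 with 15. Separate runs put the loss at SD 0 at no more than about 1 point.

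**5. After a sample size increase.** At 232 Subjects (20 and 40 sites, SD 0 to 1.0), the planned test and the CMH test by separate sites both have 97 to 99% power.

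**The case against.** The strongest reply is that nothing planned is lost. The sample size was derived from the unstratified test, that test keeps 80 to 83% power in the scenarios run, its error is not inflated by site differences, and at 232 Subjects the choice hardly matters. This stands, and it limits the point to efficiency.

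A reader might infer that the limits are too wide whenever sites differ at all. The figures do not support that. At SD 0.5 to 0.7 with 25 or 40 sites, coverage of the planned interval was 94.7 to 95.1%, and any power difference was mostly within simulation error. A reader might also infer that stratified randomisation calls for a test over all 40 sites; step 3 shows that this would lose about 6 points of power if sites are alike.

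Three practical objections also have force:

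- With 40 sites, merging those under 6 Subjects puts about 60% of Subjects in one stratum (84% if sites are of equal size). That is why the gain there is only 1 to 2 points. The cut-off of 6 is a choice and has no source in the documents.
- The usual Mantel-Haenszel interval can under-cover when the risk difference varies by site. Coverage was 89 to 95% across scenarios; with 15 sites at SD 1.2 it was 93.3%, against 95.6% for the planned interval.
- The interim in SAP 8.7 would have to use the same statistic.

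The objection that SAP 7.4 already deals with site does not stand. That section asks whether the treatment effect varies between sites, not whether response rates do. Its consequence is optional, depends on the data, and leaves the primary test unchanged.

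**Conclusion.** The design and the primary analysis do not match, and no other section closes the gap. The planned test is valid and adequately powered on its own assumptions, but it becomes conservative and forgoes efficiency when sites differ substantially. At a logit SD of 0.5 or less the effect is negligible. At 1.0 to 1.2 the two-sided error is about 3 to 4% and about 2 to 4 points of power are forgone, with about 2 the most to expect at 40 sites.

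These sizes depend on the assumed between-site SD, block size and site sizes, none of which the documents give; an SD of 1.0 already implies a wide spread of site response rates. The documents do not support reading this as an invalid test, an inflated error rate or an insufficient sample size. It is a cheap improvement.

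**What to change.** In SAP 8.5.1, and in Protocol 4.7.1.1 to match:

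- Make the primary test a Cochran-Mantel-Haenszel test stratified by site. Merge small sites by a rule based on enrolment counts alone and fixed before unblinding, for example all sites with fewer than 6 Subjects.
- Report a stratified risk difference, and name an interval method shown by simulation to hold its coverage when the risk difference varies by site.
- Keep the unstratified binomial test as a sensitivity analysis.

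In SAP 8.7, use the same statistic for conditional power and in the cited sample size re-estimation procedure. State how the merging rule works across the two stages, because sites can pass the cut-off between them.

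In SAP 7.4, say that the poolability result does not change the primary test.

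The cost is a few lines of SAP text and code, slightly more work at the interim, and up to about 1 point of power if sites do not differ.

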8.5.2. Supporting Analyses

The primary efficacy endpoint will also be analyzed in the Per-protocol and Completer cohorts.

8.6. Secondary Efficacy Endpoints (SEE)

The hypotheses will be tested utilizing an overall Type I error of 5%. The overall Type I error will be maintained by utilizing Hochberg's method to test the collection of the first five secondary objectives. These will be tested only if the primary efficacy endpoint is met. Secondary efficacy endpoints will be analyzed in the Per Protocol population.

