7.2. Missing Data and Sensitivity Analyses

The primary efficacy endpoint will be assessed in the ITT Cohort, consisting of all randomized Subjects not in the Surgical Roll In Cohort, with missing endpoint assessments examined in sensitivity analyses. Secondary efficacy endpoints will be assessed in the population of Subjects with complete data (baseline and at the Primary Endpoint Assessment Visit). Sensitivity analyses of the impact of missing data will include a tipping point analysis for the primary efficacy endpoint where the endpoint is computed with possible combinations of imputed success and failure for Subjects with missing primary efficacy assessment. Additionally, for the primary and secondary efficacy endpoints, a last observation carried forward analysis will be conducted.

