8.2. Study Populations

Several Cohorts are defined.

Intent to Treat (ITT) Cohort consists of all randomized Subjects who are not in the Surgical Roll-In group. This is the primary analysis population for the primary efficacy endpoint. The primary efficacy endpoint will be assessed in the ITT cohort. Additionally, the following analysis populations are defined. The primary efficacy endpoint will also be assessed in the per-protocol and completer cohorts. The secondary efficacy endpoints will also be assessed in the ITT cohort.

Surgical Roll In Cohort consists of all Subjects implanted in the Surgical Roll In group.

Per-protocol: Subjects within the ITT cohort receiving the correct randomized treatment, meeting the enrollment criteria, compliant with delivery of stimulation at least 80% of the maximum possible sessions delivered, and who have no other major protocol deviations affecting the primary endpoint evaluation will be considered to be part of the Per Protocol population.

Completers: All randomized Subjects who complete the Primary Endpoint Assessment Visit and associated endpoint assessments, regardless of compliance with the delivery of stimulation or the requirement to maintain constant medications.

Crossover Cohort: All Subjects in the Crossover Group who met the inclusion criterion 2 for low back pain (Low Back Pain VAS of ≥ 6.0 cm and ≤ 9.0 cm (on a 10cm scale)) and inclusion criterion 3 for ODI (Oswestry Disability Index score $\geq 21\%$ and $\leq 60\%$) at the time of crossover.

The primary efficacy endpoint and secondary efficacy endpoints will also be assessed in the Per-protocol and Completer cohorts.

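### The SAP assigns the five Hochberg-tested secondary endpoints to the Per Protocol set in 8.6, names other sets in 7.2 and 8.2, and never says which one carries the confirmatory test

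*SAP*

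**What the plan says.** For the secondary endpoints, the SAP names analysis sets in three places:

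- **SAP 8.6** gives the Hochberg rule and the gate on the primary endpoint, then closes the paragraph with "Secondary efficacy endpoints will be analyzed in the Per Protocol population". The sentence carries no qualifier.
- **SAP 7.2**: "Secondary efficacy endpoints will be assessed in the population of Subjects with complete data", meaning baseline and the Primary Endpoint Assessment Visit. It adds: "Additionally, for the primary and secondary efficacy endpoints, a last observation carried forward analysis will be conducted".
- **SAP 8.2**: "The secondary efficacy endpoints will also be assessed in the ITT cohort". It later adds: "The primary efficacy endpoint and secondary efficacy endpoints will also be assessed in the Per-protocol and Completer cohorts".

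For the primary endpoint the ranking is clear. SAP 8.2 says of the ITT Cohort: "This is the primary analysis population for the primary efficacy endpoint". SAP 8.5.2, headed Supporting Analyses, says: "The primary efficacy endpoint will also be analyzed in the Per-protocol and Completer cohorts".

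SAP 8.2 defines Per Protocol as the part of the ITT Cohort that received the assigned treatment, met the entry criteria, was "compliant with delivery of stimulation at least 80% of the maximum possible sessions delivered", and had no other major deviation bearing on the primary endpoint.

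SAP 6.2 and 8.6.1–8.6.5, and protocol Table 1, 4.7.2 and 4.7.2.1, give the hypotheses, tests or Hochberg rule without naming a set.

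**The concern.** After the primary endpoint, these five tests are the only claims with controlled type I error. The text can be read in two ways, and each has a cost. The two costs are alternatives and do not add.

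- **If 8.6 governs**, the superiority tests run in a set defined by what happened after randomisation (session compliance and deviations). The comparison is then no longer protected by randomisation. If exclusion is related to outcome differently in the two arms, the result is biased, and the bias could favour either arm.
- **If 8.6 does not govern**, no set is fixed, and the one reported as confirmatory could be chosen after the results are known. Hochberg controls error within one family in one set. It does not cover a choice among sets.

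**Working it through.** **1. The wording, side by side**

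| SAP section | Set for the secondaries | Ranked? |
|---|---|---|
| 7.2 | Complete data at baseline and endpoint visit | No |
| 8.2, first statement | ITT ('also') | No |
| 8.2, last statement | Per Protocol and Completers ('also') | No |
| 8.6 | Per Protocol | No, but placed with the Hochberg rule |
| 8.2 and 8.5.2, primary endpoint | ITT primary; Per Protocol and Completers supporting | Yes |

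'Also' means in addition to something. In 8.2 it is attached to ITT, Per Protocol and Completers in turn, so none of them is marked as the base. SAP 7.2 may be only a complete-case rule within whichever set applies; in that case it does not settle the question either.

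**2. The plan's sample size, used to size the illustration**

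With 50% vs 25%, two-sided 5%, 80% power and pooled proportion 0.375:

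n per arm = [1.960 × √(2 × 0.375 × 0.625) + 0.842 × √(0.25 + 0.1875)]² / 0.25² = (1.342 + 0.557)² / 0.0625 ≈ 57.7, so 58 per arm and **116 in total**. This matches SAP 6.1; power at 58 per arm is 80.2%. Attrition: 116 × 1.10 = 127.6, so 128, or 64 per arm.

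**3. Illustration of size**

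The documents give no compliance rate, exclusion rate or correlation between endpoints. The following are assumptions.

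- 64 per arm, all five secondary nulls true, endpoints correlated 0.6 through one shared factor.
- Tests as planned: three t-tests, one Mann-Whitney on seven categories, one two-proportion test (20% prevalence assumed).
- Hochberg: claim at least one endpoint if, for the ordered p-values, any p(i) ≤ 0.05/(6 − i), i.e. 0.01, 0.0125, 0.0167, 0.025, 0.05.
- Per Protocol drops the lowest 5%, 10% or 20% per arm (3, 6 or 13 of 64) on a latent compliance variable. Its association with the shared outcome factor is 0, or 0.3–0.5, set separately by arm.
- 40,000 trials per scenario; simulation standard error 0.001–0.0015.

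Family-wise error before the gate on the primary (target 0.05; ITT gives 0.038–0.043):

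| Exclusion in Per Protocol | 5% | 10% | 20% |
|---|---|---|---|
| Tracks poor outcome, Treatment only | 0.045–0.047 | 0.046–0.059 | 0.062–0.098 |
| Tracks poor outcome, Control only | 0.043–0.046 | 0.049–0.057 | 0.063–0.098 |

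Across the three exclusion rates, exclusion unrelated to outcome gives 0.038–0.042, and equal tracking in both arms gives 0.042–0.047.

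Direction matters. At 20% exclusion, false claims in favour of the device are 0.055–0.095 with Treatment-only tracking and 0.004–0.008 with Control-only tracking, against 0.020 in ITT.

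**4. Effect of the gate on the primary endpoint**

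The gate is an ITT win on the primary, whose latent value is correlated 0.6 with the secondaries. The rates below are false device-favouring secondary claims.

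- Null primary (25% vs 25%): at most 0.011, against 0.003–0.004 in ITT.
- Real primary effect (50% vs 25%): about 0.02 in ITT and with unrelated exclusion. With Treatment-only tracking: 0.028–0.033 at 5%, 0.034–0.048 at 10% and 0.054–0.093 at 20%.

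The gate therefore protects little once the primary truly works, which is when these claims would be made.

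**5. The other reading: set not fixed**

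With exclusion unrelated to outcome, and a win accepted in any of ITT (64 per arm, fully observed), complete data (58 per arm) or Per Protocol within complete data, family-wise error is 0.061–0.071 before the gate. A separate calculation with correlation 0 to 0.7, completers 90–95% and Per Protocol 60–85% of ITT gives 3.4–5.1% for one pre-named set and 5.3–9.6% for any of three.

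**The case against.** The strongest reply is that 8.6 does settle the matter. It is the only place that joins alpha control to a set, and it does so in one unqualified paragraph. SAP 7.2 can be read as a complete-case rule inside that set, and ITT as an addition to Per Protocol fits the first 'also' in 8.2. Only the closing sentence of 8.2, which makes Per Protocol an addition too, stands in the way.

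Several further points have force:

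- If 8.6 governs, there is no free choice of set.
- Family-wise error clearly exceeds 0.05 only with about 20% exclusion and one-arm tracking, and the documents show neither. Both arms have the same device instructions and visit schedule (protocol 4.8), and the same encouragement and counselling below 90% compliance (protocol 6.5–6.7).
- The simulation models one compliance variable. The defined set also excludes on eligibility, treatment received and other deviations.
- The three-set figure needs ITT to be fully observed. Without imputation, ITT and complete data coincide. The two-set figure is then 0.052, 0.054 and 0.059 at 5%, 10% and 20% exclusion, an excess of only 0.002–0.009.
- The planned ITT, Completer and LOCF analyses would make any divergence visible.

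These points limit the size of the problem but do not remove it. Accepting 8.6 as governing means accepting confirmatory superiority tests in a post-randomisation subset. Differential exclusion is also plausible. Protocol 4.9 expects the Treatment group to be mostly unblinded and Control about half, and protocol 7.2 lists painful contraction among the stimulation risks, while Control receives minimal pulses. Displaying several results does not say which one the Hochberg decision uses.

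**Conclusion.** The concern holds as a defect of specification. The SAP ranks its sets for the primary endpoint and not for the five alpha-controlled secondaries, and the one set placed beside the Hochberg rule is selected after randomisation. Confidence in the inconsistency is high. Bias is not shown and could run in either direction.

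On the assumed inputs there is no inflation at 5% exclusion, little at 10%, and up to 0.098 at 20% with one-arm tracking. Under the other reading, choosing among sets gives roughly 0.05–0.07 at correlation 0.6, depending on whether two or three distinct sets are in play, and up to 0.096 under the wider assumptions. These figures illustrate the mechanism; they do not predict what this trial will show.

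The ITT primary and trial success are untouched, and the secondaries are tested only after the primary is met. It should be fixed, but it does not threaten the trial's main conclusion.

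**What to change.** Before unblinding:

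1. In SAP 8.6, replace the Per Protocol population with the ITT Cohort, analysed as randomised, as the single set for the Hochberg tests.
2. Align 7.2 and 8.2 with this, and label the Per Protocol and Completer analyses of the secondaries supportive, as 8.5.2 already does for the primary. While editing 8.2, say whether Completers are limited to the ITT Cohort; as worded they could include randomised Surgical Roll In Subjects.
3. Name one primary missing-data method for the secondaries and keep LOCF as a sensitivity analysis. Multiple imputation from earlier visits is one option: VAS is collected at Visits 5–7, and ODI, EQ-5D, Percent Pain Relief and SGIC at Visit 7. If it is chosen, state how the Mann-Whitney results will be combined, since rank tests have no routine pooling rule.

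The cost is wording in three SAP sections and the programming for the missing-data method. No new data or visits are needed, and Subjects explanted before day 120 are already followed to that visit (protocol 6.16). The downside is that the ITT estimate may be slightly smaller than the effect in compliant Subjects. Items 1 and 2 resolve the inconsistency by themselves; item 3 makes the ITT analysis fully specified.
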